5.2 Conflict of Interest

Members of the DMC should remain independent of the study. Prior to their participation on the DMC, the members will be asked to sign a form disclosing any conflicts of interest, whether scientific, financial, or other, and will be required to notify the Sponsor or designee of any changes that occur during their participation on the DMC.

Members of the DMC, and their immediate families, will not buy, sell, or hold stock, options, derivatives or any other financial instrument related to the Sponsor's company for the following periods: from the date applicable to the member's first DMC meeting until the first to occur of the following: (a) the last meeting of the DMC; (b) the study results are made public; or (c) until a year after the member's active personal involvement in the DMC ends.

Certain other activities are not viewed as constituting conflicts of interest but must be reported annually to the Sponsor: the participation of a member in educational activities supported by the Sponsor and occasional scientific consulting to the Sponsor on issues not related to the product in the study.

5.3 Confidentiality

All members of the DMC will treat all reports, meeting discussions, minutes, and recommendations of the DMC as confidential.

5.4 Reimbursement

DMC members will receive an honorarium for their time and effort on the committee. DMC members will be reimbursed for reasonable expenses related to attending DMC meetings, such as transportation, lodging, and meals. No other payment or future consideration will be provided.

5.5 Indemnity

DMC members will be indemnified by the Sponsor from third party claims relating to harm arising to study participants or other parties as a result of such DMC members' actions and decisions taken in good faith in accordance with the terms of this Charter. The foregoing shall not apply in the case of harm caused by the negligence or wrongful conduct of a DMC member.

6. RESPONSIBILITIES OF THE SPONSOR

The Sponsor is responsible for supplying safety and efficacy information to the DMC, Regulatory Authorities, and the Investigators. The Sponsor's responsibilities include the following:

1. Assure the availability of resources to the DMC so that the DMC may fulfill its responsibilities as described in this Charter.
2. Review the DMC recommendations. The Sponsor has the ultimate responsibility for all final decisions concerning whether or not the DMC recommendations will be implemented.
3. The Sponsor will be the responsible party for the design and conduct of the study, and regulatory reporting of SAEs in accordance with the applicable regulations.

The Sponsor Contact, identified in [Appendix 2](#), or their designee, will be responsible for the following:

1. Review DMC recommendations and arrange for Sponsor review and decision.
2. Serve as a resource to the DMC for requests of additional data or other information.
3. Be available to address safety issues that occurred in the study.
4. Attend the open sessions of all DMC meetings.
5. On a monthly basis, ensure that the DMC Secretary is provided with a monthly cumulative SAE listing with event narratives from the study for distribution to the DMC.
6. Ensure that the DMC Secretary is provided with a cumulative SAE listing with event narratives for inclusion with the DMC Data Report prior to any DMC safety data review meeting.

7. RESPONSIBILITIES OF THE DMC ADMINISTRATOR AND DMC SECRETARY

The Sponsor will engage a DMC Administrator and DMC Secretary to aid in planning, organizing, and coordinating DMC activities, disseminating meeting reports, and communicating between the DMC and the Sponsor. The DMC Administrator and DMC Secretary will sign a confidentiality agreement for their participation in the DMC activities. The DMC Administrator and DMC Secretary for the study listed in [Appendix 2](#).

The DMC Administrator is responsible for the following:

1. Develop and facilitate the review and signing of the DMC Charter.
2. Plan, organize, and coordinate DMC activities in accordance with the established DMC Charter, including timely delivery of study data (e.g., DMC Data Reports).

3. Provide administrative and logistic services to the DMC, serving as the primary contact point for day-to-day operations and between the DMC and the Sponsor.
4. Plan, organize, and host each of the DMC meeting open sessions.
5. Provide periodic progress status reports of the DMC activities to the Sponsor as needed.

The DMC Secretary will assist the DMC Administrator and is responsible for the following:

1. Forward the DMC Data Reports, monthly cumulative SAE listings and narratives, and any safety-related information to the DMC members. Materials will be forwarded at least 5 business days before any scheduled DMC meeting or teleconference, and as soon as possible before any ad hoc teleconference, when applicable.
2. Attend both the open and closed sessions of the DMC meetings. Produce, distribute for review, and finalize DMC meeting minutes for each meeting, separately for the open and closed sessions (see [Section 8.7](#)).
3. Facilitate drafting of the Recommendations Letter based on the meeting minutes (see [Section 8.6](#)).
4. Maintain a secure central file of all data reports, all minutes, and all DMC Recommendation Letters submitted to the Sponsor.
5. Provide an archived copy of all maintained files to the Sponsor after the study database is locked and the DMC activities have concluded.

8. DMC MEETINGS

The DMC meetings are planned to either be face-to-face or via teleconference (see [Appendix 3](#) for schedule). The DMC will participate in an initial (kick-off) meeting ([Section 8.1](#)) and at least 9 safety data review meetings ([Section 8.2](#)). At the first data review meeting, the DMC will review subject safety and will also review efficacy data from study CT-AMT-061-01 and confirm the dose of AMT-061 to be used in study CT-AMT-061-02 ([Section 9](#)). Subsequent data review meetings will focus on subject safety and assessment of the impact of NABs and will occur approximately every 6 months during subject enrollment and then every 12 months until both studies have completed or have been terminated. Meetings focused on the impact of NABs will be organized as needed depending on the rate of subject enrollment.

Ad hoc meetings may take place if requested by the DMC or Sponsor ([Section 8.8](#)).

8.1 Kick-off Meeting

The initial (kick-off) meeting of the DMC will be held prior to enrolment of the first subject in the trials and will be an open meeting to provide the DMC with an understanding of the study expectations and to establish the DMC procedures. At the meeting, the DMC members will meet with Sponsor representatives to discuss both of the studies, review and finalize the DMC Charter, and discuss the proposed content of the DMC Data Report (see [Section 11](#)). Additional topics which may be discussed include: the frequency of meetings, the format of future meetings, specific analyses approaches, key safety variables to be reviewed for decision making, and the potential need for additional meetings. The DMC Charter will be finalized and signed off shortly after the meeting.

The DMC Chair approves the DMC Charter on behalf of the DMC. The DMC Charter must be approved prior to start of screening of subjects. Once the approved DMC Charter is accepted by all DMC members by signature, the DMC will be considered activated.

8.2 DMC Safety Data Review Meetings

The DMC will participate in at least 9 safety data review meetings. DMC data review meetings will consist of two open and one closed session. The DMC Secretary will record both open and closed sessions, and prepare minutes of the meeting (see [Section 8.7](#)).

8.2.1 Open Session I

The first open session will be hosted by the DMC Administrator and will include the DMC members, DMC Secretary, Sponsor representatives (may include the Principal Investigator), and the Study Biostatistician. At the open session, the Sponsor's representative(s) and study personnel involved in trial management will present an overview of the study's current progress status to the DMC. The open session should focus on the conduct and progress of the trial with special attention to safety and efficacy data. Data presented in the open session may include data on enrolment data, individual adverse events, baseline characteristics, and subjects lost to follow-up.

8.2.2 Closed Session

The closed session will be led by the DMC Chair and will only include the members of the DMC and the DMC Secretary.

The Sponsor's representative(s) as well as study personnel involved in trial management will leave the meeting/teleconference prior to the start of the closed session. The DMC closed session will begin once the DMC Secretary confirms only the attendees for the closed session are on the teleconference web-link and telephone call-in line; connections to the session will be monitored during the session to ensure the closed nature of the discussion.

Prior to the meeting, the DMC Data Report and other safety information will have been provided to the DMC via the DMC Secretary for their review.

During the closed session, the DMC members will discuss the provided data summaries and formulate their recommendations to the Sponsor.

DMC members have the right to request detailed information regarding any of the reported individual clinical endpoint events if deemed necessary. The Sponsor Contact and Study Biostatistician will be "on call" during the DMC closed session, in case the DMC requests additional safety information and/or needs to discuss statistical considerations of the provided data; the Study Statistician will maintain confidentiality concerning these discussions.

8.2.3 Open Session II

At the conclusion of the closed session, the open session attendees will be invited to rejoin the meeting/teleconference for a second open session. This second open session will be hosted by the DMC Administrator and will include the DMC members, DMC Secretary, and the Sponsor Contact at a minimum. At this session, the DMC will share their

recommendations with the Sponsor Contact and other Sponsor representatives who are present. Concerns or questions from the DMC may be addressed at this time as well.

8.3 Quorum

For a meeting to proceed, a quorum of three (3) DMC members is required at each safety data review meeting.

At the beginning of the open sessions, the DMC Administrator will confirm the attendance of the quorum. If the quorum is not met, the Chair will confirm that the DMC meeting should not proceed and the DMC Administrator will reschedule the meeting.

The quorum at an ad hoc data review meeting will be three (3) DMC members.

8.4 Voting

All 4 DMC members have voting privileges. To vote, a DMC member must be a participant in the DMC meeting. Voting is by voice and will be recorded by the DMC Chair and in the closed portion of the meeting minutes.

DMC members are responsible for voting on the following:

- All recommendations that will be submitted to the Sponsor (see **Section 8.5**).

A unanimous vote by all members is required for all recommendations to implement a modification to the conduct of the study(ies), to temporarily halt enrollment, or to stop the study(ies).

Any recommendations to modify the study's conduct (e.g., early termination of the study due to alarming safety concerns) must be agreed upon by all members of the DMC and will be made on the basis of the provided study safety data.

A simple voting majority at a meeting will be required for a routine proposal, motion, or recommendation to be made to the Sponsor that does not involve modification to the conduct of the study or discontinuation of the study.

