5.1 DMC Membership

The DMC will consist of 4 non-sponsor, independent voting members who have been approved by the Sponsor and the SC. They will be physicians and clinicians with expertise in the area of hemophilia. Each DMC member will be considered and recognized as an expert in his/her fields of practice and will be experienced and knowledgeable with the conduct of clinical trials. DMC members may not participate in the study as Investigators and are not

allowed to knowingly administer medical or any other type of care to any subject in the study during the study conduct.

One member (1) will be designated as the Chair of the DMC. The Chair will be the primary contact for the DMC with the Sponsor, SC, and Principal Investigator, communicating through the DMC Administrator, and will also lead the discussions during the closed sessions of the DMC safety data review meetings (see [Section 8.2.2](#)).

It is understood that the DMC members will be available to fulfill the DMC obligations for the entire planned 5 year period of the two studies specified in this Charter, until the studies are completed or terminated, and the final required DMC meeting has occurred and safety data have been reviewed by the DMC. In the event that a DMC member has to stop his/her participation in the DMC, it will be determined by the Sponsor in consultation with the DMC Chair if a replacement will be required. If a replacement is deemed required, they will be selected by the Sponsor and the SC. No replacement can be made without the approval of the Sponsor.

The members of the DMC are identified in [Appendix 1](#).

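### Does a quorum of three leave the DMC unable to recommend a halt or stop, when the charter asks for unanimity of all four members?

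*SAP*

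**What the plan says.** One DMC charter, included with the SAP, governs both this trial and the Phase III trial CT-AMT-061-02.

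- **Membership (5.1).** "The DMC will consist of 4 non-sponsor, independent voting members". If one leaves, "it will be determined by the Sponsor in consultation with the DMC Chair if a replacement will be required".
- **Quorum (8.3).** "a quorum of three (3) DMC members is required at each safety data review meeting". For unscheduled meetings: "The quorum at an ad hoc data review meeting will be three (3) DMC members". Below that number, "If the quorum is not met, the Chair will confirm that the DMC meeting should not proceed and the DMC Administrator will reschedule".
- **Voting (8.4).** "To vote, a DMC member must be a participant in the DMC meeting". Then: "A unanimous vote by all members is required for all recommendations to implement a modification to the conduct of the study(ies", and the same sentence covers pausing enrollment and stopping. The next sentence deals with modifications of conduct, gives early termination as its example, and says these "must be agreed upon by all members of the DMC". Routine recommendations need only a simple majority at the meeting.

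**The concern.** The charter allows a meeting to be held that cannot deliver the recommendations for which a DMC mainly exists. If three members attend and all three want to pause enrollment, the literal text gives them three votes where four are needed. The absent member cannot vote, and the charter text has no proxy or written ballot. The rescheduling rule in 8.3 is not triggered, because the meeting is quorate. The steps in 8.5 (immediate notice to the Sponsor, recruitment on hold after a stop recommendation) begin only once the DMC has made its recommendation.

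A looser reading, unanimity of those taking part, would let the 3-0 vote stand, so the same vote could be treated in two ways. What is at stake is the speed of a safety action. In Phase III, enrollment continues while a modification is put in place unless a temporary stop is also recommended (8.5), and that stop needs the same vote.

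**Working it through.** **1. What a three-member meeting can do.** Inputs: 4 voting members (5.1, 8.4), quorum 3 (8.3), only participants vote (8.4).

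- Attendance patterns that meet the quorum: C(4,3) + C(4,4) = 4 + 1 = 5.
- Patterns that can give four votes: 1.
- Largest vote with three present: 3, which is less than 4.

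So on the literal reading the observation is correct.

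**2. How often a quorate meeting is one short.** The documents give no attendance rate. If each member attends independently with an assumed probability p, the share of quorate meetings that lack a member is 1 − p⁴ / [p⁴ + 4p³(1−p)] = 1 − p / (4 − 3p).

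| Assumed p | Share with three members |
|---|---|
| 0.80 | 1 − 0.80/1.60 = 50.0% |
| 0.90 | 1 − 0.90/1.30 = 30.8% |
| 0.95 | 1 − 0.95/1.15 = 17.4% |

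Three-member meetings could therefore be common. The problem also needs that meeting to be the one that votes for a protective action, and the documents give no basis for estimating that.

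**3. Whether 8.3 and 8.4 conflict.** They do not. Section 8.3 says when a meeting may be held, and 8.4 says how many must agree to a particular decision. A three-member meeting can review data, make routine recommendations and discuss a halt. The wording also favors one reading: the routine rule is tied to those at the meeting, while the strict rule refers to all members and, for modifications, to the whole committee. Four of four is the natural meaning.

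**4. What can follow a 3-0 vote.**

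- The Chair can call an emergency meeting at any time on a safety question (8.8).
- Ad hoc meetings can be requested by the DMC or by the Sponsor (section 8), and section 10 provides for them on a safety concern, affected outcomes or the need for a protocol amendment.
- Teleconference is an accepted format (section 8).
- The second open session directly follows the closed one with the Sponsor Contact present, and DMC concerns may be raised there (8.2.3).
- The Sponsor makes the final decision on any recommendation (section 6) and may suspend this trial for any reason (Protocol 10.1.5).

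**5. How long the wait could be.** Scheduled safety reviews are about 6 months apart during enrollment and 12 months apart afterwards (section 8, Appendix 3). To wait that long, three members would have to vote to halt or stop and then neither they, the Chair nor the Sponsor would call a meeting. During enrollment there are also neutralizing-antibody reviews about every 10 subjects (section 10, Appendix 3). With about 56 Phase III subjects that is 56/10 = 5.6, so roughly five or six occasions if they are not combined. Once all subjects are enrolled and the 12-month interval applies, there is no enrollment left to halt. The realistic delay is the time needed to reach the fourth member.

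**6. Where the weight falls.** Planned subjects: 3 here, possibly 6 (4.2), and about 56 in Phase III (4.3).

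- 56/(56 + 3) = 94.9%
- 56/(56 + 6) = 90.3%

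The temporary enrollment stop listed in 8.5 names only CT-AMT-061-02. In this trial the first scheduled data review follows the six-week interim data (section 9, Appendix 3), when the planned subjects have already had their single dose.

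**The case for a change.** The strongest case for a change is that a stopping rule should have one reading, settled before it is needed, and that one or two sentences would settle it. The routes above are all optional: nothing obliges anyone to reconvene, no time limit is set, and an ad hoc meeting also has a quorum of three, so it could end one vote short again. A departed member need not be replaced, yet 8.4 still speaks of four.

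The facts in this stand; the inference is weaker. Each available wording either adds little or gives something up:

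- **Requiring a teleconference after a 3-0 vote** makes compulsory a step the charter already permits and that three members who have just voted to halt would take anyway. It still waits for the fourth member.
- **Counting only participants** lowers the threshold from four of four to three of three at such a meeting. That is faster, but a stop recommendation, which puts recruitment on hold, could then issue without the fourth member's view. If the fourth member agrees, the two rules differ only in timing. If the fourth member would dissent, they give different answers, and nothing in the charter suggests that the stricter one was unintended.

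After an unreplaced departure, the sensible reading of all members is those then serving.

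**Conclusion.** No change to the plan is called for. On the literal text a 3-0 vote cannot become a modify, halt or stop recommendation that day, and the charter leaves the next step to the people involved. That is a procedural gap a working DMC fills by convening its fourth member; it is not a contradiction between 8.3 and 8.4. Unanimity of the full committee for disruptive recommendations is a fair trade of some speed for full agreement.

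The expected cost is a short delay, and it falls mainly on Phase III. For this trial, with three single-dose subjects and descriptive analyses only, it changes no estimate, summary or conclusion.

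This rests on two assumptions: that after a unanimous three-member vote someone with the power to call a meeting would do so, and that the fourth member can be reached by teleconference. The Phase III protocol is not among the documents, so any suspension rules of its own could not be checked. If the Sponsor revises the charter for other reasons, a clarifying phrase in 8.4 would do no harm, but nothing here requires one.

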8.5 DMC Recommendations

Based upon their review and discussion of the safety data at each meeting, the DMC has the responsibility to recommend to the Sponsor whether the study should proceed as planned, be modified, or be stopped.

Anticipated recommendations are as follows:

- Continue the studies according to the protocols and current amendments.
- Temporarily stop enrollment in the CT-AMT-061-02 study to investigate a safety issue.
- Modify the study protocol(s) and/or the informed consent.
- Stop the studies due to an urgent situation (serious safety issue).

If the DMC detects a safety signal or has concerns about the provided data in the DMC Data Report or other safety information, they may request additional safety-related information from the Sponsor Contact or designee.

Modifications recommended by the DMC may include, but are not limited to, changes in the exclusion criteria due to NABs (see [Section 10](#)), other changes in the inclusion/exclusion criteria, frequency of safety monitoring, and instituting changes in the study procedures. While modifications are put into place, enrollment would continue in the CT-AMT-061-02 study unless the DMC also recommends for a temporary stop.

In the case that the DMC recommends to stop the studies or to temporarily halt enrollment in CT-AMT-061-02, the DMC Chair will notify the Sponsor Contact immediately. If the Sponsor needs additional clarification, the Sponsor Contact, or designee, and the DMC members will meet as quickly as possible to discuss the recommendations.

If the DMC recommends to stop the studies, the Sponsor's response would be to place study recruitment on hold pending final decision by the Sponsor. Investigators, Institutional Review Boards (IRBs), and other Regulatory Authorities will be notified by the Sponsor, as appropriate.

8.6 Recommendation Letter

Following each safety data review meeting, the DMC will submit a letter to the Sponsor outlining their recommendations for the study. The DMC Secretary will facilitate the drafting of the letter, based on the DMC recommendations discussed and agreed upon during the closed session. If there is a recommendation for action, the brief rationale for such recommendation will be included in the letter. The DMC Recommendation Letter will be sent to the DMC Chair for review, approval, and signature following the meeting (no later than 1 working day after the DMC meeting). The DMC Secretary will then provide a copy of the final signed Recommendation Letter to the Sponsor Contact, Principal Investigator, and the DMC Administrator on the DMC Chair's behalf via email. If the recommendation letter is not provided to the Sponsor on the same day as the meeting, the DMC Secretary will provide the Sponsor with the DMC members' recommendation decision via email.

The Sponsor will be responsible for communicating to the Investigators, IRBs, and/or other regulatory bodies, as appropriate, a summary of the DMC recommendation(s) and the Sponsor's proposed action.

